FITZPATRICK SKIN TYPE CLASSIFICATION SCALE: The Fitzpatrick Skin Type Classification Scale is a numerical classification schema for human skin color developed in 1975 by Harvard Medical School dermatologist, [name], PhD. The scale classifies a person's complexion and their tolerance of sunlight.

The Fitzpatrick Classification Scale classifies skin type from I through VI according to the applicable criteria contained in the chart below.

Skin Type	Skin Color	Characteristics
I	White; very fair; red or blond hair; blue eyes; freckles	Always burns, never tans
II	White; fair; red or blond hair; blue, hazel, or green eyes	Usually burns, tans with difficulty
III	Cream white; fair with any eye or hair color; very common	Sometimes mild burn, gradually tans
IV	Brown; typical Mediterranean Caucasian skin	Rarely burns, tans with ease
V	Dark Brown; mid-eastern skin types	Very rarely burns, tans very easily
VI	Black	Never burns, tans very easily

POOLABILITY EVALUATION

The primary efficacy outcome is a binary variable, with success defined as a 30% or greater reduction in self-reported Degree of Pain rating on the 0-100 VAS from baseline to study endpoint evaluation. Poolability analysis for this primary binary outcome will be via the Breslow-Day test for homogeneity of odds ratios.

Furthermore, poolability analysis will also be conducted for the continuous outcome of mean change from baseline to study endpoint in self-reported Degree of Pain ratings on the 0-100 VAS through a treatment-by-subgroup interaction term applying a logistic regression model that also includes the main effect terms of all treatment groups.

SAFETY ANALYSES

Safety analyses will be based on all subjects who were randomized to the test or to the placebo procedure group. Safety will be assessed by evaluating and comparing frequency and incidence of observed and/or reported adverse events between test and placebo procedure groups. A chi-square test with a continuity correction will be performed to compare the percentage of subjects who had adverse events between test and placebo group subjects.

CASE REPORT FORMS

The case report forms that will be used to collect the data from each subject in this clinical study can be found in **Appendix E**.

REFERENCES

ⁱ Bocock MG, Collier JM, McNair PJ, Simmonds M, Larmer PJ, Armstrong B. A framework for the classification and diagnosis of work-related upper extremity conditions: systematic review. *Semin Arthritis Rheum*. 2009;38:296-311.

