Subjects will be recruited from three different sites and among the licensed health care provider's test site's pool of patients who are currently being treated for, or who are seeking treatment for Lateral Epicondylitis, or from patients who respond to the following recruitment materials, if needed.

Flyer

WANTED

ADULTS WITH LATERAL EPICONDYLITIS, ONGOING
FOR ONE MONTH, FOR A CLINICAL STUDY
OF THE EFFECTS OF LOW-LEVEL LASER LIGHT ON REDUCING LATERAL
EPICONDYLITIS.

**THIS STUDY INVOLVES SIX LASER LIGHT PROCEDURES, TWO TIMES A WEEKS FOR
THREE WEEKS WITH THE MULTI RADIANCE MEDICAL® MR5® LASER AT THE TEST
SITE.**

THERE IS THREE VISITS PRIOR TO LASER LIGHT PROCEDURES WITH ONE MORE
VISIT TO THE TEST SITE
ONE MONTH AFTER THE LAST LASER LIGHT PROCEDURE.

YOU WILL RECEIVE \$450 IF YOU FINISH THE STUDY.

FOR MORE INFORMATION PLEASE CONTACT:

<PI name>
<test site name & location>
<phone # and/or e-mail>

Newspaper Ad

**Lateral Epicondylitis
Research Study**

This study is to see if the Multi Radiance Medical® MR5® LASER, a non-invasive, investigational device that uses low-level laser light, can help to relieve symptoms of Lateral Epicondylitis pain longer than one month in duration.

The study involves ten visits to a test site and recording some information at home.

You will receive \$450 if you finish the study. Please contact
<PI name> at
<test site name & location> at
<phone and/or e-mail> for details.

Compensation

A subject will be paid a stipend of \$450.00 USD for their participation in the study upon completion. Subjects will not be charged for the cost of the study procedures administered with the Multi Radiance Medical® MR5® Prototype Device for the cost of any other directly related evaluations or measurements that occur as part of his or her participation in the study.

Sample size

There will be 60 subjects evaluated for eligibility in this clinical study:

- 30 subjects in the active procedure group
- 30 subjects in the control procedure group (Placebo)

Rationale for sample size

Based on the following parameters established for the purposes of assessing efficacy of the Multi Radiance Medical MR5 Prototype Device in this clinical study using the Fischer's Exact test to assess the primary endpoint.

- Individual subject success criteria is defined as a 30% or greater reduction in self-reported Degree of Pain rating on the 0-100 VAS from baseline to study endpoint evaluation.

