- Overall study success criteria of at least a 30% difference between the test device group and the placebo group, comparing the proportion of individual successes in each group.
- It is anticipated that about 50% of subjects in the test device group and about 20% of subjects in the placebo group will meet the individual success criteria, and
- Intended application of a two-tailed test with an alpha value of 0.05 and Power of 0.8

- the sample size of 25 available subjects per group (test group and the control group, separately) has been determined using the following reference calculator: *Hypothesis Testing: Categorical Data - Estimation of Sample Size and Power for Comparing Two Binomial Proportions* in Bernard Rosner's *Fundamentals of Biostatistics*.

For the purposes of sample size calculation, a subject loss-to-follow-up of 20% is anticipated.

Therefore, a minimum starting sample size of 30 evaluable subjects in each group is needed to ensure that a sufficient number remains at the end of the trial (25 subjects per group) for any significant differences found between groups to be considered statistically valid and representative of the general population being sampled. This results in a total of 60 subjects being enrolled in this study across both study procedure groups.

RANDOMIZATION

Subject allocation to procedure group will be via variable block randomization with varying block sizes of two and four used at random to minimize the likelihood of predicting the next procedure group assignment. In addition, randomization will be stratified by Fitzpatrick Skin Type grouping

Randomization will be attained using computer generation sequence methodology, ensuring that the randomization methodology and the generated allocation sequence is concealed from the investigator and subjects.

Concealment will be insured as follows:

- Each computer-generated randomization sequence is unique and will therefore not be able to be replicated.
- Randomization will occur to either 'Test Group A' or 'B' rather than to a tests or placebo group, and only the study Sponsor will know which assignment corresponds to the active devices and which corresponds to the fake device. The Sponsor will not reveal this information to any source (investigators, subjects, or study Monitor) until the final study data analysis is complete.

TRIPLE BLIND DESIGN

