The pre-procedure assessment phase will commence following successful completion of the individualized pain management regimen stabilization phase and just prior to commencement of the procedure administration phase.

CONTINUED STUDY ELIGIBILITY EVALUATION

Prior to the subject commencing the Pre-Procedure Assessment phase of the study, the investigator will:

- review the subject's recordings of use/application of his or her individualized pain management regimen to ensure it was correctly applied and recorded, and that there are no deviations significant enough to warrant withdrawal of the subject from the study prior to entry to the pre-procedure assessment phase; and
- calculate the average of the 3 VAS degree of pain scores recorded during the last three days of the individualized pain management regimen stabilization phase. In order for the subject to proceed, the 3-day average VAS score must be 50 or greater. If it is less than 50, the subject's participation in the study ends at this time.

PRE-PROCEDURE MEASURES

- Degree of Pain Rating. This will occur within 15 minutes prior to the initial procedure administration. The exact time the VAS rating is recorded will be noted.
- PRTEE, Grip Strength and TNFa measurements will be noted.

PRE-PROCEDURE VARIABLES

- Baseline concomitant medication and treatment/therapy use
- Historical pain medication and treatment/therapy use
- Baseline Lateral Epicondyle pain variables
- PRTEE, Grip Strength and TNFa measurements and Fitzpatrick Skin Type Classification will be noted.
- Demographics

PROCEDURE ADMINISTRATION PHASE

PROCEDURE ADMINISTRATION PROTOCOL

- The procedure administration phase of the study will commence within 15 minutes subsequent to completion of the pre-procedure assessment phase.
- The procedure administration phase comprises a total of six procedure administrations with the Multi Radiance Medical® MR5® Prototype Device: two

procedures a week for three consecutive weeks*, each procedure administration three to four days apart.

[figure not shown]
- *Three weeks, 2 times a week... Follow-up at 4th week after administration phase*

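### The planned 60 is described as screened in one place and enrolled in another, the stratification plan fills at 50, and nothing allows for subjects who fail an eligibility check before treatment

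*Combined protocol and SAP*

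**What the plan says.** The combined protocol and SAP states the planned size in three places.

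- **Sample size:** "There will be 60 subjects evaluated for eligibility in this clinical study". The bullets directly below divide this number by arm, beginning with "30 subjects in the active procedure group" and giving the same number to placebo.
- **Rationale for sample size:** "Intended application of a two-tailed test with an alpha value of 0.05 and Power of 0.8", with success rates of 50% and 20% and Fisher's exact test, leads to "the sample size of 25 available subjects per group". Then "For the purposes of sample size calculation, a subject loss-to-follow-up of 20% is anticipated", so "a minimum starting sample size of 30 evaluable subjects in each group is needed". The section concludes: "This results in a total of 60 subjects being enrolled in this study across both study procedure groups".
- **Sample Stratification:** recruitment and enrolment by Fitzpatrick skin type are planned for 50 subjects, with a table by site, arm and skin type. A category that is full at a site takes no further subjects there.

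The Table of Subject Events gives the order: consent, qualification evaluation, randomization, stabilization phase, continued eligibility evaluation, first procedure. Continued eligibility requires a satisfactory review of regimen use and a 3-day average VAS of at least 50. On the VAS requirement: "If it is less than 50, the subject's participation in the study ends at this time".

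Under the Intent to Treat (ITT) Principle, the primary analysis takes randomized subjects with a valid baseline who had at least the first procedure.

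**The concern.** The number screened, the number enrolled and the number treated are the same only if nobody fails an eligibility check, and the plan contains two such checks. The first, the qualification evaluation, comes before randomization. The second comes after it, so a subject can be randomized and counted as enrolled, then leave before treatment and fall outside the primary analysis set. Imputation does not bring such a subject back, because the analysis set requires a first procedure.

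The plan gives no failure rate for either check and no screening target. It does not say whether the 20% is meant to cover failures at the second check. Sites therefore have no single count that tells them when recruitment is complete, and the one closing rule they do have fills at 50. At stake is the number of subjects behind the primary comparison, in a trial whose sample is already small for its stated power.

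**Working it through.** **Inputs.** From the Rationale for sample size: success 50% versus 20%, two-sided alpha 0.05, power 0.8, Fisher's exact test, 25 per group at the end, 30 per group at the start, 20% loss. From Sample Stratification: the site table. Assumed, because the documents give no figure: 10 to 40% of those screened fail across the two checks combined.

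**1. The plan's own 25 per group.** It does not reproduce. The usual two-proportion formula with these inputs gives 39 per group, or 45 with continuity correction. By exact enumeration, Fisher power is 0.796 at 43 per group and 0.802 at 44. At 25 per group it is 0.51.

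**2. The step from 25 to 30.** 25 × 1.2 = 30, which is the stated figure. Allowing for 20% loss requires 25 / 0.8 = 31.25, so 32. Run forward, 30 × 0.8 = 24 per group. So 24, not 25, remain even if nobody fails a check.

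**3. The site table.** Test arm: (7+5) + (4+3) + (4+2) = 25. Placebo arm: (8+4) + (4+3) + (4+2) = 25. The total is 50. After 20% loss, 25 × 0.8 = 20 per group.

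**4. If 60 are only screened.** With f the combined failure proportion, starters per group = 30 × (1 − f) and completers per group = starters × 0.8. Power is two-sided Fisher by exact enumeration, with completers rounded to the nearest whole subject.

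| f (assumed) | Starters per group | Power if all starters are analysed | Completers per group | Power on completers |
|---|---|---|---|---|
| 0% | 30 | 0.596 | 24.0 | 0.493 |
| 10% | 27 | 0.550 | 21.6 (22) | 0.432 |
| 20% | 24 | 0.493 | 19.2 (19) | 0.395 |
| 30% | 21 | 0.403 | 16.8 (17) | 0.319 |
| 40% | 18 | 0.359 | 14.4 (14) | 0.260 |

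At 20 per group (step 3) power is 0.41. The column for all starters matters because the primary analysis keeps treated dropouts by imputation. It takes the 50% and 20% rates as unchanged by imputation.

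**5. If 60 are randomized.** Only failures at the second check count. If 10% failed it (assumed), 27 per group would start and 21.6 would complete, as in the 10% row.

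**6. Number to screen for 60 to reach treatment.** 60 / (1 − f), rounded up: 67, 75, 86 and 100 for f = 10, 20, 30 and 40%.

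**The case against.** The strongest reply is that the screening phrase is a slip. People who have only been screened have no arm, yet the line is followed at once by a 30/30 split, and the rationale calls the 60 a starting sample and enrolled. A reader might infer from the phrase that the trial will screen 60 people and stop. The documents do not say so, and 60 allocated subjects is the likelier intent.

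That reply does not settle the matter. The enrolled reading still leaves the post-randomization check without an allowance, and the only written closing rule fills at 50, not 60. The 50 might be meant as the expected completers, since it equals 25 per group. But the section speaks of recruitment and enrolment, and a cap on enrolment cannot be set by who later completes.

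Three further points on the other side stand:

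- The qualification evaluation is itself the first check, so only one check follows it.
- The analysis set with imputation keeps treated dropouts, so the 20% loss does not simply reduce the number in the primary test. That is why both power columns are shown.
- Any loss beyond the drop to 24 depends on a failure rate that the documents do not give.

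**Conclusion.** The point holds as an inconsistency in a figure the trial relies on. The planned number is 60 screened, 60 enrolled or 50 enrolled, depending on the section, with no allowance for failures at either check.

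On the plan's own numbers, without any assumption about failures, 60 yields 24 completers per group and 50 yields 20, against the 25 stated. Fisher power is 0.49 and 0.41, against 0.51 at 25. If 60 were only screened and 10 to 40% failed, completers would be about 22 to 14 per group with power 0.43 to 0.26. If imputation keeps every treated subject, 27 to 18 per group give 0.55 to 0.36, against 0.60 at 30.

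Two stronger conclusions might be inferred and are not supported. One is that 60 cannot leave roughly 25 per group: with no failures it leaves 24. The other is that correcting the label restores the claimed power. It does not, because 25 per group gives 0.51 and about 44 are needed for 0.8. That larger shortfall is a separate defect in the sample-size calculation.

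**What to change.** - **Sample size and Rationale for sample size:** use one definition in both, replacing the screening phrase: 60 subjects who pass the continued eligibility evaluation and receive the first procedure. Give the split as about 30 per group. An exact quota per arm cannot be guaranteed, because the second check follows randomization in blocks of two and four.
- **Recruitment rule:** state that screening continues until that number is reached, and that the 20% loss applies from the first procedure onward.
- **Expected completers:** restate as 24 per group.
- **Sample Stratification:** reconcile the 50-subject table and its closing rule with the 60, so that filled categories do not end enrolment early.

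**Cost:** changes to the protocol text and the stratification table; the target of 60 stays. More than 60 people may have to be screened and randomized (for the assumed 10 to 40% failure, 67 to 100 screened), and recruitment may take longer.

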- *Tipping Point Analysis:* Tipping point analysis will be used to examine the impact of missing data on the study conclusion. Tipping point analysis is defined as the difference in means (for continuous data) or the difference in the number of events (for binary data) between treatment groups in the missing cohort at which the study conclusion is changed. A tipping point analysis replaces the missing value with other values so that the resulting p-value is equal to the pre-specified significance level (i.e. $\alpha=0.05$, 2-sided).
- *Multiple Imputation Analysis:* Multiple imputation analysis is a strategy to handle missing values in a clinical trials wherein each missing value is replaced with a set of plausible values that represent the uncertainty about the right value to impute. Multiple imputation does not attempt to estimate each missing value through simulated values, but rather to represent a random sample of the missing values. This process results in valid statistical inferences that properly reflect the uncertainty that results from missing values, such as valid confidence intervals for parameters.

Multiple imputation inference involves three distinct phases:

1. The missing data are filled in m times to generate m complete data sets.
2. The m complete data sets are analyzed by using standard statistical procedures.
3. The results from the m complete data sets are combined for the inference.

Multiple imputation usually assumes that the data are missing at random (MAR). That is, for a variable Y , the probability that an observation is missing depends only on the observed values of other variables, not on the unobserved values of Y .

Pre-Protocol Analysis will also be performed for the set of all subjects who were randomized to procedure group and completed the study according to the full protocol.

Primary analysis of efficacy will be according to intent to treat (ITT) analysis through the application of:

- 1) **Fisher's exact test** to compare the proportion of success between the test and the control groups, considering that randomization has been diligently conducted and important covariates between the two groups are well balanced.

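### The stated 80% power is not delivered: 25 evaluable subjects per arm give about 51% power with the named Fisher's exact test at 50% vs 20%, and 30 per arm less 20% loss leaves 24, not 25

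*Combined protocol and SAP*

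**What the plan says.** The Rationale for sample size gives every input needed to check its result.

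- **Endpoint:** binary. "Individual subject success criteria is defined as a 30% or greater reduction in self-reported Degree of Pain rating on the 0-100 VAS" from baseline to the study endpoint.
- **Test:** the design parameters are set for "using the Fischer's Exact test to assess the primary endpoint". The Statistical Analysis section again names Fisher's exact test as the first primary analysis, "to compare the proportion of success between the test and the control groups".
- **Assumed rates:** "about 50% of subjects in the test device group and about 20% of subjects in the placebo group" are expected to meet the criterion. The Overall Study Success Criteria paragraph repeats these rates.
- **Error rates:** "Intended application of a two-tailed test with an alpha value of 0.05 and Power of 0.8".
- **Result:** "the sample size of 25 available subjects per group (test group and the control group, separately) has been determined", with a textbook two-binomial-proportions calculation cited as the source.
- **Loss:** "a subject loss-to-follow-up of 20% is anticipated". The section concludes that starting with 30 per group leaves 25 per group at the end, for 60 in total.

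The Sample stratification distribution plan then builds its site and skin-type table on 50 subjects, that is, 25 per arm.

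**The concern.** A 30-point difference between 50% and 20% is large, but 25 per arm is few for a two-sided test of two proportions at 80% power. Fisher's exact test is also conservative in small samples, so it needs more subjects than the simple formula suggests. The step from 25 to 30 looks like a 20% mark-up (25 × 1.2), which does not offset a 20% loss.

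The results are intended to support a De Novo submission, and study success is defined on the difference in proportions. If the true power is near 50%, the trial has about an even chance of missing the very effect it assumes. A non-significant result from a trial labelled as 80% powered could then be read as evidence against the device, when the design was simply too small to tell.

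**Working it through.** **Inputs**, all from the Rationale for sample size: p1 = 0.50, p2 = 0.20, two-sided alpha 0.05, power 0.80, 1:1 allocation, Fisher's exact test, 20% loss.

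**1. Attempt to reproduce 25 with the type of formula cited.**

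n = [z(α)·√(2·p̄·q̄) + z(β)·√(p1·q1 + p2·q2)]² / (p1 − p2)², where p̄ = (0.50 + 0.20)/2 = 0.35.

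- √(2 × 0.35 × 0.65) = √0.455 = 0.6745
- √(0.25 + 0.16) = √0.41 = 0.6403
- Two-sided: (1.960 × 0.6745 + 0.8416 × 0.6403)² / 0.09 = 38.5, so **39 per arm**
- With continuity correction, (n/4)·[1 + √(1 + 4/(n × 0.30))]² at n = 38.48: 44.9, so **45 per arm**
- One-sided, with 1.645 in place of 1.960: 30.2, so **31 per arm**

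Other standard variants give 36 (unpooled variance) and 38 (arcsine) two-sided, and 29 and 30 one-sided. None gives 25. The uncorrected two-sided formula does return 25 if power is set to 60%. The documents do not say how 25 was obtained.

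**2. Power at 25 per arm.**

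- Normal approximation: (0.30 × √25 − 1.960 × 0.6745)/0.6403 = 0.278, and Φ(0.278) = 60.9%.
- Fisher's exact test: sum the binomial probabilities, at 50% and 20%, of every 2×2 table with a two-sided p-value at or below 0.05.

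| Per arm | Fisher power at 50% vs 20% |
|---|---|
| 24 | 49.3% |
| 25 | 51.0% |
| 30 | 59.6% |
| 39 | 73.2% |
| 43 | 79.6% |
| 44 | 80.2% |
| 45 | 81.5% |

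Requiring in addition the protocol's observed difference of at least 30 points does not help: the joint probability is 50.5% at 25 per arm, 46.7% at 24 and 56.1% at 30.

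**3. Effect for which 25 per arm does give 80% power.** With 20% success on placebo, Fisher power at 25 per arm is 78.8% at 60% success on the device and 81.0% at 61%. The design is therefore powered for about 61% vs 20%.

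**4. Loss to follow-up.**

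- 30 × (1 − 0.20) = 24, not 25
- 25 / (1 − 0.20) = 31.25, so 32 per arm to keep 25
- 25 × 1.20 = 30 gives the protocol's figure

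This slip costs about 2 points of power (51.0% to 49.3%). The unsupported 25 is the main fault.

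**The case against.** The arithmetic is hard to contest, since all inputs are stated and no other section corrects the figure. The stronger arguments concern its consequence.

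- **The ITT analysis fills in missing data, so 24 may not be the analysed number.** This is fair: treated drop-outs stay in the denominator. But 30 per arm with no loss gives only 59.6%. The ITT set also excludes anyone without a valid baseline or a first procedure. Subjects are randomized before the stabilization phase and leave if their 3-day mean VAS falls below 50, so some randomized subjects cannot be recovered. The schedule lists no VAS rating between the pre-procedure one and the endpoint, so LOCF would carry baseline forward and count the subject as a failure. As an illustration, assume that all of the 20% loss is of this kind: the rates become 0.8 × 50% = 40% and 0.8 × 20% = 16%, and Fisher power at 30 per arm is 44.7%.
- **An ANCOVA on VAS change is also listed under the primary analysis.** If responder status reflected a normal change score with equal variances, which the documents do not state, 50% vs 20% would imply a standardised difference of about 0.84. A two-sample t-test would then have about 83% power at 25 per arm. This limits the even chance of a miss to the binary test. It does not rescue the calculation: the section sizes the trial on Fisher's test, success is defined on proportions, and no mean difference or SD is given.
- **A near-miss such as 12/25 vs 5/25 (p = 0.072) proves little.** This stands. The difference is 28 points, so it fails the 30-point criterion whatever the p-value, and 13/25 vs 5/25 gives p = 0.038. The finding rests on the power figures and not on such examples.
- **The assumed rates are only approximate.** A gap between 50% and 61% on the device is not rounding.

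**Conclusion.** The concern holds. On the protocol's own inputs, 25 evaluable per arm gives 51.0% power with the two-sided Fisher's exact test, and 24 per arm gives 49.3%, against a stated 80%. The test first reaches 80% at 44 per arm, and no standard formula, one- or two-sided, gives 25. The loss step is also wrong as written, but minor. These figures assume true rates of exactly 50% and 20%, independent subjects and equal arms. They apply to the binary endpoint on which the trial is sized, and not to the ANCOVA. Because the error lies in the main justification of the design, it must be corrected.

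**What to change.** Rewrite the Rationale for sample size so that it states:

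- 25 evaluable per arm gives about 51% power, and 24 per arm about 49%, for 50% vs 20% with a two-sided Fisher's exact test at 0.05;
- 80% power at 25 per arm corresponds to about 61% vs 20%;
- with 20% loss, 30 enrolled per arm leaves 24, and keeping 25 takes 32.

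This costs protocol wording only, and the stated power becomes less favourable. It makes the document accurate but does not remove the shortfall.

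Enlarging the trial is the sponsor's choice. Power of 80% at 50% vs 20% needs 44 evaluable per arm; at 20% loss that is 44/0.8 = 55 enrolled per arm, 110 in total. The 50-subject stratification table would then have to be rebuilt. Whichever course is taken, the claim that 25 per arm gives 80% power at these rates has to go.
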